## Fibroscan®

Where available, Fibroscan® will be performed as per institution standard practice at Visits 3 and 9. The data collected on the Fibroscan form (liver stiffness measured in kPa and controlled attenuation parameter [CAP] measured in dB/m) will be converted to determine stage of fibrosis and grade of steatosis, respectively, using a score card [4,5] as outlined in the table below.

Fibroscan Scoring for Cholestatic Liver Disease (Fibrosis Score):

Score	F0 to F1 No scarring/ Mild fibrosis	F2 Moderate fibrosis	F3 Severe fibrosis	F4 Cirrhosis or Advanced fibrosis
FibroScan Result	2 to 7 kPa	>7 to 9 kPa	>9 to 17 kPa	>17 kPa

**CAP Score & Steatosis Grading:**

CAP Score	Amount of Liver with Fatty Change	Steatosis Grade
<238 dB/m		S0
238 to 260 dB/m	11 to 33%	S1
260 to 290 dB/m	34 to 66%	S2
> 290 dB/m	≥67%	S3

### Markers of Fibrosis

APRI score and Fib-4 score will be calculated at randomization and at end of treatment.

APRI = [(AST in U/L) / (AST ULN in U/L)] × 100 / (Platelets in 10^9/L)

Fibrosis 4 Score = (Age\*AST in U/L) / (Platelets in 10^9/L \* √(ALT in U/L)).

### Global Impression of Change and Global Impression of Symptom Measures

Patients ≥8 years of age, caregivers, and clinicians will complete the global impression of change (GIC) and the global impression of symptoms (GIS) measures at randomization (Visit 3; GIS only), Visits 4 and 6, and at EOT (Visit 9). The GIC items assess change in itch (patient version), scratching (caregiver and clinician versions), and sleep (all versions) since starting the study drug. The GIS items assess itch (patient version), scratching (caregiver and clinician versions), and sleep (all versions) in the past week.

A detailed description of procedures and assessments to be conducted during this study is summarized in the schedule of study assessments in [Table 1](#) below.

**Table 1: Schedule of Study Assessments**

Study Activity	Screening Period		Treatment Period								Follow-Up
			Random-ization	Phone Contact	4 weeks	8 weeks	12 weeks	18 weeks	22 weeks	24 weeks	
Study Days	-56 – (-35) ±2	-28 – (-7) ±2	0	14 ±3	28 ±3	56±3	84±3	126 ±3	154 ±3	168 ±3	196 ±3
Visits	Clinic Visit 1	Clinic Visit 2	Clinic Visit 3	n/a	Clinic Visit 4	Clinic Visit 5	Clinic Visit 6	Clinic Visit 7	Clinic Visit 8	Clinic Visit 9/EOT a	Clinic Visit 10 b
Informed consent c	X										
Inclusion/exclusion criteria	X		X								
Demographics	X										
Concomitant medication d	X	X	X	X	X	X	X	X	X	X	X
Medical and surgical history	X		X								
Physical examination including voluntary photography	X		X				X			X	
Skin examination	X		X		X		X			X	X
Vital signs e	X	X	X		X	X	X	X	X	X	X
eDiary: itching, scratching, and sleep scores f	Daily diary entry										
Clinical chemistry g	X		X		X	X	X	X		X	X
Hematology g			X		X	X	X	X		X	X
Urinalysis g		X					X			X	
Serum bile acids h	X	X	X		X	X	X	X	X	X	X
INR		X			X		X		X		X
Autotaxin i			X		X					X	

Study Activity	Screening Period		Treatment Period								Follow-Up
			Random-ization	Phone Contact	4 weeks	8 weeks	12 weeks	18 weeks	22 weeks	24 weeks	
Study Days	-56 – (-35) ±2	-28 – (-7) ±2	0	14 ±3	28 ±3	56±3	84±3	126 ±3	154 ±3	168 ±3	196 ±3
Visits	Clinic Visit 1	Clinic Visit 2	Clinic Visit 3	n/a	Clinic Visit 4	Clinic Visit 5	Clinic Visit 6	Clinic Visit 7	Clinic Visit 8	Clinic Visit 9/EOT a	Clinic Visit 10 b
p-C4 i			X		X					X	
AFP			X							X	
Vitamins A & E b		X					X			X	
25-hydroxy vitamin D			X				X			X	
Blood sample for A4250 PK i					X					X	
Abdominal Ultrasound			X							X	
Fibroscan ® (where available)			X							X	
QoL questionnaire (PedsQL)			X							X	
Patient/Caregiver/Clinician Global Impression of Change					X		X			X	
Patient/Caregiver/Clinician Global Impression of Symptoms			X		X		X			X	
Pregnancy test l	X i	X	X		X	X	X	X	X	X j	X
Study drug dispensed k			X		X	X	X	X	X		
Adverse events l	Continuous collection										
Study drug compliance					X	X	X	X	X	X	

AFP: alfa-fetoprotein; BMI: body mass index; eCRF: electronic case report form; eDiary: electronic diary; EOT: End of Treatment; ICF: informed consent form; INR: international normalized ratio; p-C4: plasma 7 $\alpha$  Hydroxy 4-cholesten-3-one; PedsQL: Pediatric Quality of Life Inventory; QoL: quality of life; RR: respiratory rate; s-BA: serum bile acid; PK: pharmacokinetics.

- a Must also be performed at the time a patient is prematurely withdrawn from the study. This visit is the same as Visit 1 in the extension protocol (Study A4250-008).
- b Assessments must be performed 28 days following the final dose of study drug. This visit is omitted if patients are entering Study A4250-008.
- c The ICF (and assent) must be signed before any study procedures are performed.
- d Past (within 1 month prior to Visit 1) and current medication will be documented in the eCRF.
- e Includes blood pressure, pulse, RR, temperature, height (or length depending on age), and body weight (using a certified weight scale). BMI will be calculated.
- f Includes training on use of the device at Screening (Visit 1) and review of patient daily entries during 14 days prior to Clinic Visit 3 to determine eligibility.
- g See [protocol Table 3](#) for detailed parameters.
- h Patients will fast (water intake only is permissible) for at least 4 hours prior to the collection of samples for s-BA and vitamin A. Exceptions can be made for infants, less than 12 months of age, if unable to fast for the full 4 hours. All s-BA results during the treatment period and follow-up will be blinded.
- i Samples will not be collected for patients  $\leq 10$  kg. In the event of an SAE, a PK sample should be collected as close to the onset of the event as possible.
- j For girls who have reached menarche. Serum test at Visit 1; urine test at other visits. A serum pregnancy test will also be conducted at Visit 9 for patients entering Study A4250-008. If a urine pregnancy test is positive, a serum pregnancy test should be performed to confirm the pregnancy.
- k Study drug to be taken once daily on Day 1 through Day 167 as described in [protocol Section 8.2](#)
- l Adverse event information will be collected from the time of signing of the ICF to study discontinuation.

## 4 STUDY ENDPOINTS

### 4.1 Primary efficacy endpoints

The primary efficacy endpoints are as follows:

- **Europe (EU) and rest of the world (RoW):** Proportion of patients experiencing at least a 70% reduction in fasting s-BA concentration from baseline to the end of treatment or reaching a level  $\leq 70$   $\mu\text{mol/L}$  after 24 weeks of treatment.

Fasting s-BA baseline will be calculated as the average of the last 2 values prior to the first dose. The end value is the average of the values at Weeks 22 and 24 after the start of double-blind treatment. If a patient's baseline value is  $\leq 70$   $\mu\text{mol/L}$ , then only the criterion of at least 70% reduction in fasting s-BA concentration will be used to determine whether the patient is a responder or not for the primary endpoint analysis.

- **United States (US):** Proportion of positive pruritus assessments at the subject level over the 24-week treatment period based on the Albireo ObsRO instrument.

A positive pruritus assessment is defined as a scratching score of  $\leq 1$  or at least a one-point drop from baseline on the Albireo ObsRO instrument. At each assessment, the AM score will be compared to the baseline AM average, and the PM score will be compared to the baseline PM average. Both AM and PM pruritus assessments will be included in the analysis of this endpoint. AM scores from the period of 14 days prior to or on the first dose day of study medication will be averaged as AM baseline. PM scores from the period of 14 days prior to the first dose day of study medication will be averaged as PM baseline. If a patient's baseline average score is  $\leq 1$ , then only the criterion of a one-point drop from baseline on the Albireo ObsRO instrument will be used to determine whether a pruritus assessment is positive or not for the primary endpoint analysis.

### 4.2 Secondary efficacy endpoints

The secondary efficacy endpoints include the following:

- **EU and RoW:** Proportion of positive pruritus assessments at the subject level over the 24-week Treatment Period based on the Albireo ObsRO instrument.
- **US:** Proportion of patients experiencing at least a 70% reduction in fasting s-BA concentration from baseline to the end of treatment or reaching a level  $\leq 70$   $\mu\text{mol/L}$  compared to placebo after 24 weeks of treatment.

- **All Regions:**

All other secondary endpoints are compared to placebo.

- Change from baseline to Week 12 and to Week 24 in fasting s-BA
- Change from baseline to Week 12 and to Week 24 in serum ALT concentration
- Change in growth from baseline to Week 12 and to Week 24, defined as the linear deficit (height for age, weight for age and MBI for age) compared to a standard growth curve (Z-score, SD from P50)
- Proportion of responders for pruritus scores at Weeks 12 and 24 based on the ObsRO instrument. For pruritus scores, a responder is defined as a patient achieving a reduction in score equivalent to or exceeding the clinically meaningful threshold established from the blinded psychometric analysis (Pruritus Evidence Dossier).
- Change in sleep parameters measured with the Albireo PRO and ObsRO instruments by each 4-week interval over the 24-week treatment period
- Proportion of individual assessments meeting the definition of a positive pruritus assessment at the subject level over the 24-week treatment period as reported on the Albireo PRO instrument. A positive pruritus assessment includes an itch score  $\leq 1$ , or at least a one-point drop from baseline based on the Albireo PRO instrument; only patients  $\geq 8$  years of age will complete the Albireo PRO instrument
- Proportion of individual assessments meeting the definition of a positive pruritus assessment at the subject level from Weeks 0-4, Weeks 0-8, Weeks 0-12, Weeks 0-18, Weeks 0-24, respectively, and the proportion of positive pruritus assessments at each 4-week interval as reported on the Albireo ObsRO instrument. A positive pruritus assessment is defined as a scratching score of  $\leq 1$  or at least a one-point drop from baseline on the Albireo ObsRO instrument. At each assessment, the AM or PM score will be compared to the baseline AM or PM average, respectively.
- Proportion of individual AM assessments meeting the definition of a positive pruritus assessment at the subject level from Weeks 0-4, Weeks 0-8, Weeks 0-12, Weeks 0-18, Weeks 0-24, respectively, and the proportion of positive pruritus assessments at each 4-week interval as reported on the Albireo ObsRO instrument. A positive pruritus assessment is defined as a scratching score of  $\leq 1$  or at least a one-point drop from baseline on the Albireo ObsRO instrument. At each assessment, the AM score will be compared to the baseline AM average.
- Proportion of individual PM assessments meeting the definition of a positive pruritus assessment at the subject level from Weeks 0-4, Weeks 0-8, Weeks 0-12,

Weeks 0-18, Weeks 0-24, respectively, and the proportion of positive pruritus assessments at each 4-week interval as reported on the Albireo ObsRO instrument. A positive pruritus assessment is defined as a scratching score of  $\leq 1$  or at least a one-point drop from baseline on the Albireo ObsRO instrument. At each assessment, the PM score will be compared to the baseline PM average.

- Number of patients undergoing biliary diversion surgery or liver transplantation
- Number and percent of patients achieving positive pruritus assessment for more than 50% of the time during the 24-week treatment period

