### 6.3 Per-Protocol Analysis Set (PP)

The per protocol (PP) analysis set is a subset of the FAS and will consist of all randomized patients for whom no important protocol deviation (no deviation which may affect the study efficacy outcome) is documented. In identifying this population, important protocol deviations are defined as:

- Failure to meet the following inclusion criteria
  - Inclusion criteria (2) Patient must have a clinical genetic confirmation of PFIC-1 or PFIC-2 through identification of biallelic pathogenic variants in either the *ATP8B1* or *ABCB11* genes
  - Inclusion criteria (3) Patient must have elevated s-BA concentration, specifically measured to be  $\geq 100$   $\mu\text{mol/L}$ , taken as the average of 2 samples at least 7 days apart (Visits 1 and 2) prior to randomization
  - Inclusion criteria (4) Patient must have history of significant pruritus and a caregiver-reported observed scratching in the eDiary average of  $\geq 2$  (on 0 to 4 scale) in the 2 weeks prior to randomization
- Enrollment in spite of meeting the following exclusion criteria
  - Exclusion criteria (1) Patient with pathologic variations of the *ABCB11* gene that predict complete absence of the BSEP protein
  - Exclusion criteria (15) Patient suffers from uncontrolled, recalcitrant pruritic condition other than PFIC. Examples include, but not limited to, refractory atopic dermatitis or other primary pruritic skin diseases
- Compliance rate of  $< 80\%$  with study drug administration estimated based on CRF data

Important protocol deviations will be also identified by study team during protocol deviation review. The PP analysis set will provide supportive data for the efficacy analyses of primary and selected secondary endpoints.

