### **US primary endpoint**

- An additional method is used to calculate the proportion of positive pruritus assessments up to the last report day before or on Day 168. In other words, the denominator to calculate the proportion will be (the last report day x 2). All missing data before or on the last report day will be considered as negative assessments. This estimated proportion of positive pruritus assessments at the patient level over the 24-week treatment period based on the Albireo ObsRO instrument will be analyzed using the same approach as for the primary analysis.
- To address the concern that results from subjects with a baseline AM or baseline PM average score less than 2 may be difficult to interpret, additional supportive analysis will exclude patients from the primary endpoint analysis who have a baseline AM or baseline PM average score that rounded to 0 or 1.
- A supportive analysis of pruritus assessments as a continuous endpoint will be conducted. The analysis will be performed by considering the impact of intermittently missing data as well as intercurrent events.

The monthly (28-day) average in change from baseline for AM and PM, respectively will be calculated. There is a total of 6 monthly averages for AM assessments and 6 monthly averages for PM assessments over the 24-week treatment period. A mixed-effect model for repeated measures (MMRM) will be used to compare treatment effects at the last 28 days for AM and PM, respectively. Since missing not at random (MNAR) may occur, missing monthly average will be imputed with data from control arm completers using multiple imputation (MI). If there are subjects in the active arms who discontinued the study due to, e.g., relocation, their missing values may be imputed using active arm completers. To simplify the MI procedure, the description below only pertains to imputation using placebo completers. The MMRM model will include baseline score, treatment group, time (in month), treatment-by-baseline interaction, treatment-by-time interaction and stratification factors (i.e., PFIC type and age category). Unstructured covariance matrix will be used.

The following procedures in MI will be followed:

1. Intermediate missing values are imputed by the Markov Chain Monte Carlo (MCMC) imputation model, so only monotone missing values exist after imputation. 200 imputed data

sets will be created.

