The proportion of responders at Weeks 12 and 24 based on the ObsRO instrument will be analyzed using the same model as specified for the primary analysis for EU and RoW. The definition of the responder is a patient who reports a decrease in pruritus score from unrounded baseline equivalent to or greater than the threshold of meaningful change estimated from the blinded psychometric analysis; the results of the blinded psychometric analysis across all anchors support a threshold of a 1.0 point for AM, PM and AM and PM scratching scores. Section 8.9.1 includes more details about the blinded psychometric analysis. Specifically, the averaged pruritus score during weeks 11 and 12 and during weeks 23 and 24 will be used to calculate the proportion of patients achieving meaningful reduction at Week 12 and Week 24 from the baseline score. Similarly, the responder analysis will be conducted based on monthly scores at Week 12 and Week 24. Moreover, the analysis will be performed by AM, PM separately and AM & PM combined. For treatment completers whose last eDiary report day is before Week 24, if there is not enough eDiary data to calculate bi-weekly or monthly average scores at week 24, they will be excluded from analysis.

The proportion of individual assessments meeting the definition of a positive pruritus assessment at the subject level from Weeks 0-4, Weeks 0-8, Weeks 0-12, Weeks 0-18, Weeks 0-24, respectively, and the proportion of positive pruritus assessments at each 4-week interval over the 24-week treatment period for AM or PM, respectively will be analyzed using the same model as specified for the primary analysis for US. This analysis will be performed for PRO/ObsRO instruments separately.

The number and percent of patients achieving positive pruritus assessment for more than 50% of the time will be summarized by treatment group. Both AM and PM pruritus assessments will be included in the analysis of this endpoint. The proportion of patients achieving positive pruritus assessment for more than 50% of the time will be analyzed using the same model as specified for the primary analysis for EU and RoW. This analysis will also be performed separately for AM pruritus assessments only and PM pruritus assessments only.

A cumulative distribution function (CDF) plot showing proportions of patients achieving positive pruritus assessment for more than X% of the time, for X from 0 to 100%, by treatment group will be provided.

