
AM & PM baseline, daily, weekly and monthly score (scratching, itch severity)
	
For both the Albireo ObsRO scratching item and the Albireo PRO itch severity score:
 
A daily AM & PM score will be averaged from the 2 ratings for each day. A daily score will be considered missing if both assessments are missing.
 
A weekly score will be calculated by averaging all non-missing AM and PM scores in a week. A weekly score will be considered missing if <math>\geq 8</math> out of 14 assessments in a week are missing.
 
A bi-weekly score will be calculated by averaging all non-missing AM and PM scores in 2 weeks. A bi-weekly score will be considered missing if <math>\geq 15</math> out of 28 assessments in 2 weeks are missing.
 
A monthly score will be calculated by averaging all non-missing AM and PM scores in a month (28 days). A monthly score will be considered missing if <math>\geq 29</math> out of 56 assessments in a month are missing.

	
All non-missing AM scores from the period of 14 days prior to or on the first dose day of study medications, and all non-missing PM scores from the period of 14 days prior to the first dose day of study medications will be averaged as the AM & PM baseline score. Baseline score will be considered missing if <math>\geq 15</math> out of 28 assessments in the 14 days are missing. One thing of note:
 
Inclusion criteria #4: Patient must have history of significant pruritus and a caregiver-reported observed scratching in the eDiary average of <math>\geq 2</math> (on 0 to 4 scale) in the 2 weeks prior to randomization.
 
The pruritus score for purposes of establishing eligibility was calculated by taking the average of the worse of the two scores for each day. The values for week one were averaged and the values for week 2 were averaged. The two weekly averages were then averaged to provide a single score. If this score was <math>\geq 2</math> the pruritus eligibility requirement was met. The calculation of pruritus eligibility score is different from the calculation of the baseline pruritus score defined in the SAP.

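### The patient-reported itch endpoint counts any score of 1 or less as positive with no low-baseline rule, so a child who enters with mild self-reported itch can be positive at every assessment without improving

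*SAP*

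**What the plan says.** - **Entry floor.** SAP Section 6.3 gives inclusion criterion 4 as "Patient must have history of significant pruritus and a caregiver-reported observed scratching in the eDiary average of" at least 2 on the 0 to 4 scale. Appendix A adds that the eligibility score was "calculated by taking the average of the worse of the two scores for each day", and that it differs from the analysis baseline. The SAP states no minimum for the child's own itch score.
- **PRO rule.** Section 4.2: "A positive pruritus assessment includes an itch score" of 1 or less, or at least a one-point drop. Only patients of at least 8 "years of age will complete the Albireo PRO instrument".
- **Low-baseline rule.** Section 4.1: if the baseline average is 1 or less, "then only the criterion of a one-point drop from baseline on the Albireo ObsRO instrument will be used" to decide "whether a pruritus assessment is positive or not for the primary endpoint analysis". It names one instrument and one analysis.
- **Supportive exclusion.** Under the US primary endpoint in Section 8.6.3.1, an "additional supportive analysis will exclude patients from the primary endpoint analysis who have a baseline AM or baseline PM average score" rounding to 0 or 1.
- **Analysis.** Section 8.6.4 analyses the interval proportions, including Weeks 0-24, with the US primary model and adds: "This analysis will be performed for PRO/ObsRO instruments separately". It carries over the model and does not mention the low-baseline rule. The Appendix A entry for the proportion of positive assessments covers missing data, rounding and the denominator, and does not mention it either.

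**The concern.** The sponsor saw that a child with little scratching at baseline would meet the score-of-1-or-less criterion without improving, and guarded the ObsRO primary endpoint against it twice: with the Section 4.1 rule and with the supportive exclusion. Entry already requires appreciable caregiver-observed scratching, so low baselines are restricted on that instrument. The PRO item has no stated entry floor and, as written, neither safeguard.

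For a PRO baseline of 1, the rule as written calls scores of 0 and 1 positive and scores of 2 or more negative. It can register worsening but not improvement. Such a child adds to the proportion of success in whichever arm he or she is in and says nothing about benefit. This is the one secondary endpoint in Section 4.2 that names the patient's own itch score, and readers will set it beside the caregiver result.

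The ObsRO interval, AM-only and PM-only secondaries in Section 4.2 also restate the definition without the low-baseline rule, and the more-than-50% endpoint does not mention it.

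**Working it through.** **Inputs.** Planned assessments, with missing entries counted as negative (Section 7.1.1.1); scale 0 to 4 (Section 3.3); PRO rule (Section 4.2); low-baseline rule (Section 4.1); planning differences of 15 to 30 percentage points (Section 5).

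**1. The plan's denominator.** 168 days x 2 = 336, as stated.

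**2. Unchanged child, complete diary.**

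| Constant score | As written for PRO | With the Section 4.1 rule |
|---|---|---|
| 0 | 336/336 = 100% | 0/336 = 0% |
| 1 | 336/336 = 100% | 0/336 = 0% |
| 2, 3 or 4 | 0/336 = 0% | 0/336 = 0% |

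**3. Missing entries (assumed 5 to 20%).** The proportion for a constant score of 1 is 1 minus the missing share, so 95% down to 80%.

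**4. Scores that vary around 1 (assumed).** Take scores of 0, 1 and 2 averaging 1, with equal shares of 0s and 2s. If each share is 10%, 20% or 30%, the child is 90%, 80% or 70% positive as written, and 10%, 20% or 30% positive with the Section 4.1 rule.

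**5. Arm level (assumed counts).** If 30 to 40% of 20 patients per arm are aged 8 or over, there are 6 to 8 PRO patients per arm. Scoring one unchanged child 100% rather than 0% moves the raw arm mean by 100/8 = 12.5 to 100/6 = 16.7 points.

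**6. Dilution (assumed share).** If a share f of each arm scores the same whatever the treatment, a true difference d in the rest becomes d x (1 - f). With d = 25 points and f = 10%, 20% or 30%, this gives 22.5, 20 or 17.5 points. If those children truly never change, the Section 4.1 rule gives the same dilution, because they score 0% in every arm. What the rule changes is the inflated level, and it lets a fall from 1 to 0 count as benefit. Only excluding low baselines removes the dilution.

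**7. Why the ObsRO secondaries are included.** Eligibility uses the worse score of each day. A child scored 1 every morning and 2 every evening has an eligibility score of 2 and qualifies, with an AM baseline of 1. If nothing changes, the AM-only proportion over 24 weeks is 168/168 = 100% as written and 0/168 = 0% under the Section 4.1 rule.

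**8. Why the trigger must be fixed.** Section 4.1 refers to the baseline average; Section 8.6.3 rounds the baseline for scoring. An average of 1.3 does not trigger the rule unrounded, but rounds to 1 and does trigger it rounded. A later score of 1 is then positive in the first case and negative in the second.

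**The case against.** The strongest reply is that silence proves little. Sections 2.1 and 8.6.3 and Appendix A also state the primary ObsRO definition without the low-baseline rule, where it plainly applies. Section 7.1.1.1 points to Section 4.1 for what a positive assessment is, and the revision history describes the low-baseline handling in general terms. The sponsor may intend the rule for PRO too. That stands as a reason to call this a correctable wording problem, but it does not remove the two explicit limits in Section 4.1, to ObsRO and to the primary analysis. A programmer could defend either coding.

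Several limits on the consequence also stand. The endpoint is secondary with unadjusted p-values. Randomisation leads one to expect such children in all arms. The model adjusts for AM and PM baseline, so the raw shift in step 5 overstates what reaches the adjusted means, although a linear term cannot fully absorb a jump from 100% to 0% between unchanged baselines of 1 and 2. Exactly 100% requires every entry to be present and at 1 or less. The SAP lists only the entry criteria used for the per-protocol set, and criterion 4 also asks for a history of significant pruritus.

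The Section 4.1 rule has its own defect. A child with an unrounded baseline below 1 cannot fall a full point and is scored 0% whatever happens; with rounding, this applies to baselines that round to 0.

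A reader might infer that the EU/RoW ObsRO secondary and the US s-BA secondary would take values different from their primary counterparts. The SAP does not support this. The EU/RoW ObsRO entry carries no definition of its own and can only be derived from Section 4.1, and the SAP describes one derivation and test per statistic. For s-BA, Section 8.6.3.1 already has a sensitivity analysis excluding baselines of 70 µmol/L or less.

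**Conclusion.** The point holds as a defect in a secondary endpoint. As written, an unchanged PRO score of 1 or less is positive at every completed assessment: up to 336/336, against 0/336 under the rule the SAP adopted for the same problem on ObsRO. The expected effect is inflated proportions in all arms and a diluted difference.

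The per-child figures follow from the text. The arm-level figures rest on assumptions: 6 to 8 PRO patients per arm, and 10 to 30% of them unchanged at low baseline. The SAP does not say how many children have a PRO baseline of 1 or less, and there may be none.

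Two stronger readings are not supported. A reader might infer that the rule will reverse the PRO comparison; that would need a chance imbalance, which could favour either side. A reader might also infer that no other patient-reported check exists. Section 4.3 lists changes in PRO itch scores by 4-week interval, where an unchanged child shows zero change, and the patient versions of the global impression items also cover itch. Neither primary test is affected.

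**What to change.** 1. In Sections 4.2 and 8.6.4 and Appendix A, apply the Section 4.1 low-baseline rule to the PRO positive-assessment endpoint and to the ObsRO interval, AM-only, PM-only and more-than-50% secondaries. Judge it on that instrument's own AM or PM baseline.
2. State whether the rounded or the unrounded baseline triggers the rule.
3. Extend to PRO the Section 8.6.3.1 supportive analysis that excludes AM or PM baselines rounding to 0 or 1. This is needed because the rule replaces a ceiling with a floor for the lowest baselines.
4. At most, add a cross-reference saying that the EU/RoW ObsRO and US s-BA secondaries use the Section 4.1 derivations.

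The cost is SAP wording, one derivation flag and one further supportive table, settled before unblinding. PRO positive proportions may fall, children with the lowest baselines will score 0% in the main PRO analysis, and the supportive analysis will have fewer patients.
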